1.5 Pembrolizumab

The programmed cell death 1 (PD-1) pathway represents a major immune control switch which may be engaged by tumor cells to overcome active T-cell immune surveillance. Pembrolizumab (MK-3475) is a potent and highly selective humanized monoclonal antibody (mAb) of the IgG4/kappa isotype designed to directly block the interaction between PD-1 and its ligands, PD-L1 and PD-L2. This blockade enhances functional activity of the target lymphocytes to facilitate tumor regression and ultimately immune rejection.

1.5.1 Preclinical

Pembrolizumab strongly enhances T-lymphocyte immune responses in cultured blood cells from healthy human donors, cancer patients, and primates. In T-cell activation assays using human donor blood cells, the EC₅₀ (concentration where 50% of the maximum effect is achieved) has been ~0.1 to 0.3 nM. In addition to interleukin-2 (IL-2), tumor necrosis factor alpha (TNF α), interferon gamma (IFN γ), and levels of other cytokines were found to be modulated by Pembrolizumab. The antibody potentiates existing immune responses only in the presence of antigen and does not nonspecifically activate T-cells. Using an anti-murine PD-1 analog antibody, PD-1 blockade has been shown to significantly inhibit tumor growth in a variety of syngeneic murine tumor models. In these experiments in mice, anti-PD-1 therapy is synergistic with chemotherapeutic agents such as gemcitabine and 5-fluorouracil (5-FU) and combination therapy results in increased complete tumor regression rates in vivo.

1.5.2 Clinical experience

The importance of intact functions of immune surveillance in controlling outgrowth of neoplastic transformations has been known for decades.¹⁸ Accumulating evidence shows a correlation between tumor-infiltrating lymphocytes (TILs) in cancer tissue and favorable prognosis in various malignancies. In particular, the presence of CD8⁺ T cells and the ratio of CD8⁺ effector T cells / FoxP3⁺ regulatory T cells (T regs) correlates with improved prognosis and long-term survival in solid malignancies such as ovarian, colorectal, and pancreatic cancer, hepatocellular carcinoma (HCC), malignant melanoma (MEL), and renal cell carcinoma (RCC). Tumor-infiltrating lymphocytes can be expanded ex vivo and re-infused, inducing durable objective tumor responses in cancers such as MEL.^{19,20}

The PD-1 receptor-ligand interaction is a major pathway hijacked by tumors to suppress immune control. The normal function of PD-1, expressed on the cell surface of activated T cells under healthy conditions, is to down-modulate unwanted or excessive immune responses, including autoimmune reactions. PD-1 (encoded by the gene *Pdcd1*) is an immunoglobulin (Ig) superfamily member related to CD28 and CTLA-4 which has been

shown to negatively regulate antigen receptor signaling upon engagement of its ligands (PD-L1 and/or PD-L2).^{21,22} The structure of murine PD-1 has been resolved.²³

PD-1 and family members are type I transmembrane glycoproteins containing an IgVariable-type (V-type) domain responsible for ligand binding and a cytoplasmic tail responsible for the binding of signaling molecules. The cytoplasmic tail of PD-1 contains two tyrosine-based signaling motifs, an immunoreceptor tyrosine-based inhibition motif (ITIM) and an immunoreceptor tyrosine-based switch motif (ITSM). Following T cell stimulation, PD-1 recruits the tyrosine phosphatases, SHP-1 and SHP-2, to the ITSM motif within its cytoplasmic tail, leading to the dephosphorylation of effector molecules such as CD3 ζ , PKC θ , and ZAP70, which are involved in the CD3 T cell signaling cascade.^{22,24-26} The mechanism by which PD-1 down modulates T cell responses is similar to, but distinct from, that of CTLA-4, as both molecules regulate an overlapping set of signaling proteins. PD-1 was shown to be expressed on activated lymphocytes including peripheral CD4⁺ and CD8⁺ T cells, B cells, T regs, and natural killer cells.^{27,28} Expression has also been shown during thymic development on CD4-CD8- (double negative) T cells, as well as subsets of macrophages and dendritic cells.²⁹ The ligands for PD-1 (PD-L1 and PD-L2) are constitutively expressed or can be induced in a variety of cell types including non-hematopoietic tissues and in various tumors.^{18,30,31} Both ligands are type 1 transmembrane receptors containing both IgV- and IgC-like domains in the extracellular region and contain short cytoplasmic regions with no known signaling motifs. Binding of either PD-L1 or PD-L2 to PD-1 inhibits T cell activation triggered through the T cell receptor. PD-L1 is expressed at low levels on various non-hematopoietic tissues, most notably on vascular endothelium; whereas PD-L2 is only detectably-expressed on antigen presenting cells found in lymphoid tissue or chronic inflammatory environments. PD-L2 is thought to control immune T cell activation in lymphoid organs, whereas PDL1 serves to dampen unwarranted T cell function in peripheral tissues.³¹ Although healthy organs express little (if any) PD-L1, a variety of cancers were demonstrated to express abundant levels of this T cell inhibitor. High expression of PD-L1 on tumor cells (and to a lesser extent of PD-L2) has been found to correlate with poor prognosis and survival in various cancer types, including RCC, pancreatic carcinoma, HCC, and ovarian carcinoma. Furthermore, PD-1 has been suggested to regulate tumor-specific T cell expansion in patients with MEL.

The observed correlation of clinical prognosis with PD-L1 expression in multiple cancers suggests that the PD-1/PD-L1 pathway plays a critical role in tumor immune evasion and should be considered as an attractive target for therapeutic intervention.

Therapeutic studies in mouse models show that administration of antibodies blocking PD-1/PD-L1 interaction enhances infiltration of tumor-specific CD8⁺ T cells and leads ultimately to tumor rejection, either as a monotherapy or in combination with other treatment modalities. Anti-mouse PD-1 and anti-mouse PD-L1 have demonstrated antitumor responses as a monotherapy in models of squamous cell carcinoma, pancreatic carcinoma, MEL, and colorectal carcinoma. Blockade of the PD-1 pathway effectively promoted CD8⁺ T cell infiltration into the tumor and the presence of IFN- γ , granzyme B, and perforin, indicating that the mechanism of action involved local infiltration and

activation of effector T cell function in vivo. In-house experiments have confirmed the in vivo efficacy of PD-1 blockade as a monotherapy as well as in combination with chemotherapy in syngeneic mouse tumor models.

2. Study objectives

The overall objective of the study is to assess recommended combination dose, safety and preliminary efficacy, and predictive biomarkers for combination of regorafenib and pembrolizumab.

2.1 Primary objectives:

- The objective of the phase I part of the study is to assess safety of the combination and identification of the recommended dose (RD) for combination therapy. We will employ a 3+ 3 design with expected accrual of 3-18 patients.
- The objective of phase II part of the study is to evaluate preliminary efficacy and tolerability of the combination RD of regorafenib and pembrolizumab.

2.2 Exploratory objectives:

2.2.1 Immune effector cells:

We aim to measure the phenotype of lymphocytes and Myeloid Derived Suppressor Cells (MDSC), in pre and post-treatment blood samples and correlate these with PFS in colorectal cancer patients receiving regorafenib and pembrolizumab.

2.2.2 CtDNA and CtRNA

Changes in quantity, mutational spectrum, and functional genes with outcome.

2.2.3 SNP analysis

Predictive modeling for efficacy.

3. Investigator[s] and other study participants

1-2 other institutions will be invited to join the USC for accrual. USC will update Bayer and Merck once the other sites had agreed to be a site.

4. Study design

A standard 3+3 design will be used to escalate doses of regorafenib in combination with fixed dose pembrolizumab during the phase I part of the study. The primary goal is to identify the recommended dose (RD) of the combination.

The phase II part of the study is an open label single arm study to assess the preliminary efficacy and tolerability of the combination therapy at RD in colorectal cancer patients who had progressed or not tolerated to oxaliplatin and irinotecan based therapies. The primary endpoint is PFS, we assume that combination therapy will result in prolongation of progression free survival by 50% compared to historical PFS with single agent regorafenib. Given that PFS in CORRECT trial was 1.9 mos with type one error of 10%, power of 80% we will need a sample size of 63 pts. The expected PFS in the treatment group will be 2.85 months. The accrual is expected to happen over 24 months. Tolerability will be assessed by median duration of treatment; combination is defined to be tolerable if the median duration of treatment is at least 20% better than CORRECT data (from 1.7 months to 2.0 months).

5. Study population

5.1 Eligibility

5.1.1 Inclusion criteria

1. Patients who provided written informed consent to be subjects in this trial
2. Patients at least 18 years of age on the day of providing consent
3. Patients with histologically or cytologically confirmed advanced or metastatic colorectal cancer who had failed or are intolerant of oxaliplatin, irinotecan, and 5-FU. Patients with MSI colorectal cancer are not candidate for treatment on this trial.
4. Patients with an Eastern Cooperative Oncology Group (ECOG) performance status (PS) of 0 or 1 within 7 days of start of treatment
5. Patients capable of taking oral medication
6. Patients with evaluable or measurable lesions as per RECIST version 1.1
7. Patients with adequate organ function at the time of enrollment as defined below:
 - Neutrophil count $\geq 1200/\text{mm}^3$
 - Platelet count $\geq 7.5 \times 10^4/\text{mm}^3$
 - Hgb $> 9.0\text{g/dL}$ (transfusion > 2 weeks before testing permitted)
 - Aspartate transaminase (AST), alanine transaminase (ALT) ≤ 2.5 -times the upper limit of normal (≤ 5 -times in patients with liver metastasis)
Total bilirubin ≤ 1.5 -times the upper limit of normal
 - Creatinine ≤ 1.5 -times the upper limit of normal
 - Lipase $\leq 1.5 \times$ the ULN
 - International normalized ratio (INR) $\leq 1.5 \times$ ULN and partial thromboplastin time (PTT) or activated partial thromboplastin time (aPTT) $\leq 1.5 \times$ ULN unless receiving treatment with therapeutic anticoagulation. Patients being treated with anticoagulant, e.g. heparin, will be allowed to participate provided no prior evidence of an underlying abnormality in these parameters exists. Close monitoring of at least weekly evaluations will be

performed until INR and PTT are stable based on a pre-dose measurement as defined by the local standard of care.

8. In women with the potential for pregnancy (including patients with amenorrhea due to medical reasons, such as chemical menopause), after consenting to the study, the patient must agree to take contraception from enrollment and for at least 23 weeks after taking the final dose of the investigational drug (a period of 30 days [ovulation cycle] is added to five times the elimination half-time of I/O agent). Women with the potential for pregnancy include those who have begun menstruation, who have not undergone a hysterectomy, bilateral tubal ligation, or bilateral oophorectomy, and who have not gone through menopause. Menopause is defined as the consecutive absence of menstrual periods for ≥ 12 months. Total abstinence is an acceptable mode of contraception.
9. In the case of men, the patient must agree after consenting to the study to take contraception from enrollment and for at least 31 weeks after taking the final dose of the investigational drug (a period of 90 days [the spermatogenesis cycle] is added to five times the elimination half-time of I/O agent. Total abstinence is an acceptable mode of contraception.

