6.3.1 Dose Modification Levels

The starting dose of regorafenib is the RD. Study medication will be administered on a 2 weeks on/1 week off schedule [2 weeks out of every 3].

Doses will be delayed or reduced for clinically significant hematologic and non-hematologic toxicities that are related to protocol therapy according to the guidelines shown in the Dose Delays/Dose Modifications table that follows. Dose modifications will follow predefined dose levels. Dose adjustments for hematologic toxicity are based on the blood counts obtained in preparation for the day of treatment.

The modifications of regorafenib will follow the following predefined dose levels:		
Dose level 2	120 mg po qd	Three 40-mg tablets of regorafenib
Dose level 1	80 mg po qd	Two 40-mg tablets of regorafenib

q.d. = *quaque die* (once daily); *q.o.d.* = *quaque altere die* (every other day)

If a subject experiences more than one toxicity, dose reduction should be according to the toxicity with the highest grade

In the case of two or more toxicities of the same grade, the investigator may dose reduce according to that deemed most causally related to study treatment. For Grade 3 toxicity it is acceptable to re-challenge with same dose level at discretion of investigator if toxicity resolved to baseline or lesser grade with medical management within 7 days.

For second occurrence of the same Grade 3 toxicity dose can be reduced to 80mg q.o.d or permanently discontinue at discretion of treating investigator and the rest of the study treatment may be continued. If a dose reduction has been performed, intra-subject dose re-escalation can be considered at the discretion of the treating physician provided that the toxicity(ies) has resolved to baseline.

Tables 6-1, 6-3, and 6-4 outline dose adjustments for toxicities related to regorafenib. Dose adjustment for liver function abnormalities is discussed in table 6-5.

Table 6-1: Recommended dose modification for toxicities except hand-foot-skin reaction, hypertension and ALT/AST/bilirubin			
NCI-CTCAE v5.0^a	Dose Interruption	Dose Modification^b	Dose for Subsequent Cycles
Grade 0-2	Treat on time	No change	No change
Grade 3	Delay until \leq Grade 2 ^c	Reduce by 1 dose level	If toxicity remains < Grade 2, dose re-escalation can be considered at the discretion of the treating investigator. If dose is re-escalated and toxicity (\geq Grade 3) recurs, institute permanent dose reduction.

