In case no such decrease is seen and/or a further deterioration in liver function is seen: Administer corticosteroids (initial dose of 1-2 mg/kg prednisone or equivalent) followed by taper

If immune-related hepatitis is suspected: Directly follow guidance provided in Table 6-6

EVENT	Regorafenib	Pembrolizumab
If ALT/AST $\leq 2 \times$ ULN at baseline AND $> 5 \times$ ULN OR ALT/AST $> 2 \times$ ULN at baseline and 3 fold increase from Baseline BUT NOT EXCEEDING $8 \times$ ULN	Assess according to guidance given in Table 6-6 
 Hold until recovery to \leq G2 or baseline, then reduce 1 dose level 1st re-appearance: discontinue 	Hold and assess + decide on potential restart according to guidance given in Table 6-6
ALT or AST $> 5 \times$ ULN accompanied by a hyperbilirubinemia $\geq 2 \times$ ULN or $>50\%$ increase from total bilirubin level from baseline	Discontinue and assess according to guidance given in Table 6-6 A patient with Gilbert's syndrome should be managed according to observed elevation of ALT and/or AST if the observed bilirubin increase is below actual increased baseline bilirubin value	Hold and assess + decide on potential restart according to guidance given in Table 6-6
t-bilirubin >2 mg/dL and ALT/AST $\leq 5 \times$ ULN	No modifications	Hold and assess + decide on potential restart according to guidance given in Table 6-6
Any t-bilirubin > 3.0 mg/dL irrespective of ALT/AST values	Assess according to guidance given in Table 6-6	Hold and assess + decide on potential restart according to guidance given in Table 6-6

	
 Hold until recovery to \leq G1 or baseline, then reduce 1 dose level 1st re-appearance: Discontinue 	
AST and / or ALT > 20 x ULN	Discontinue and assess according to guidance given in Table 6-6	Discontinue and assess according to guidance given in Table 6-6

Table 6.6: Guidance on assessment and further dosing following occurrence of hepatic events of clinical interest

Assessment procedure to be applied

- Notification of Bayer and Merck within 24 hours via SAE report
- Obtain a work-up for hepatitis, including hepatitis A, B, C, D, E, EBV (Epstein-Barr virus), CMV (cytomegalovirus)
- Assess for ingestion of drugs/supplements with hepatotoxic potential and alcohol ingestion
- Assess for potential bacterial infection, biliary obstruction, or occult gastrointestinal bleeding
- Other laboratories or imaging studies as clinically indicated
- Consider liver biopsy

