- Infection needs to be ruled out with cultures of blood, urine, and ascites (if possible), as well as
- chest X-ray and abdominal imaging if relevant. If an infection is found, antibiotics should be
- started
- If biliary obstruction is present, consultation with a gastroenterologist and/or an interventional
- radiologist should be obtained to see if the obstruction may be relieved
- A careful review of drugs, including herbal and alternative medications should be obtained

Immune-related hepatitis due to study treatment should be suspected if any of the following is seen (Immune-related hepatitis is a diagnosis made after excluding other possible etiologies for the change. Viral flare (if applicable), biliary or vascular obstruction, infection, medications, and alcohol use must be ruled out):

- AST or ALT baseline values are less than $2 \times$ ULN, and AST or ALT laboratory values increase to $\geq 5 \times$ ULN
- Among patients with baseline ALT or AST $\geq 2 \times$ ULN, levels increase to $> 3 \times$ the baseline level
- AST/ALT > 500 U/L regardless of baseline level
- Among patients with baseline Tbil levels < 1.5 mg/dL: a value of > 2.0 mg/dL
- Total bilirubin > 3.0 mg/dL regardless of baseline level management
- Interrupt study treatment and alert Bayer and Merck
- Start i.v. corticosteroid (methylprednisolone 125 mg or equivalent) followed by oral corticosteroid
- Monitor with weekly laboratory tests including AST, ALT, Tbil, Dbil, ALP, and INR.

If symptoms and laboratory tests resolve to Grade ≤ 1 or baseline (if abnormal at baseline), taper steroids over 28 days. Study treatment may be restarted after steroid treatment has been tapered to prednisone ≤ 10 mg/day (or equivalent dose of another agent).

If laboratory abnormalities do not resolve within 3 weeks, or steroids cannot be lowered to ≤ 10 mg/day (or prednisone equivalent) within 12 weeks, or patients show evidence of decompensation treatment must be permanently discontinued.

For toxicity management guidelines for pembrolizumab please refer to appendix 2, section 16.2.

Prevention/management strategies for diarrhea

Diarrhea can be a common side effect of regorafenib. The preventive/management strategies for diarrhea should be consistent with local standards (e.g., anti-diarrheals and optimized hydration status).

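### For eligible baseline ALT/AST above 2.67 and up to 5 x ULN, the hold row of Table 6.5 cannot be met, because its 3-fold trigger lies above its own cap of 8 x ULN

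*Combined protocol and SAP*

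**What the plan says.** **Eligibility.** Section 5.1.1, criterion 7, sets the ALT/AST ceiling at 2.5 x ULN, raised to "5 -times in patients with liver metastasis". The synopsis repeats this.

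**Table 6.5 (section 6.3.1), first row.** The table applies to worsening liver tests considered related to regorafenib, with no alternative cause evident. The first row has two branches. With a baseline of at most 2 x ULN, the trigger is a value above 5 x ULN. With a higher baseline the condition is "ULN at baseline and 3 fold increase from Baseline BUT NOT EXCEEDING" 8 x ULN. The regorafenib action is to hold until recovery and then go down one dose level.

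**Other rows of Table 6.5.** One row discontinues regorafenib for ALT or AST above 5 x ULN with a bilirubin of at least 2 x ULN or a more than 50% "increase from total bilirubin level from baseline". One bilirubin row (above 2 mg/dL with ALT/AST at most 5 x ULN) leaves regorafenib unchanged. Another holds it for "Any t-bilirubin > 3.0 mg/dL irrespective of ALT/AST values". The last discontinues it for "AST and / or ALT > 20 x ULN".

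**General instruction above Table 6.5.** For grade 3/4 rises seen mainly under ongoing regorafenib, staff watch whether values fall within 3 days of interrupting the drug.

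**Table 6-1.** Its title limits it: "Recommended dose modification for toxicities except hand-foot-skin reaction, hypertension and ALT/AST/bilirubin".

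**Table 6.6.** Immune-related hepatitis is to be suspected, after other causes are excluded, under several triggers. One begins "Among patients with baseline ALT or AST" of at least 2 x ULN and requires a rise to more than 3 times baseline, with no upper limit. Another is AST/ALT above 500 U/L. The action is to interrupt study treatment.

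**The concern.** The elevated-baseline branch of the first row exists for patients who enter with raised transaminases. It sets a floor that moves with the baseline (3 times baseline) and a ceiling that does not (8 x ULN). Once the floor passes the ceiling, no value satisfies both. Criterion 7 admits baselines well beyond that point, and section 6.3.1 sends liver dose adjustment to Table 6.5 and not to the general toxicity table.

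A written safety rule that cannot operate for some eligible patients leaves the decision to each site. Section 13.1 asks for strict adherence, and section 3 foresees one or two further institutions. Sections 4 and 7.2 measure tolerability by the median duration of combination therapy. Different handling of the same laboratory value could therefore affect both safety conduct and that measure.

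**Working it through.** The plan gives no figure of its own to reproduce. The check is whether the row's two conditions can hold together. Let B be baseline ALT/AST in multiples of ULN, with B > 2.

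**Inputs**
- Highest eligible B: 5 with liver metastasis, 2.5 without (section 5.1.1, criterion 7).
- Trigger: 3 x B (Table 6.5, first row).
- Cap: 8 (same row).
- Next row that needs ALT/AST alone: above 20 (Table 6.5, last row).

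**Step 1: when can the row be met?** It needs 3B <= 8, so B <= 8/3 = 2.67.

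| Baseline (x ULN) | Trigger 3B (x ULN) | Within the cap of 8? |
|---|---|---|
| 2.25 | 6.75 | yes |
| 2.5 | 7.5 | yes |
| 2.67 | 8.0 | only exactly at the cap |
| 3 | 9 | no |
| 4 | 12 | no |
| 5 | 15 | no |

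**Step 2: who is affected?** Without liver metastasis the highest baseline is 2.5, where 3 x 2.5 = 7.5 <= 8, so the row works. Only patients with liver metastasis and B above 2.67 up to 5 are affected. That is (5 - 2.67)/(5 - 2) = 78% of the numerical interval from 2 to 5 x ULN. It is a share of an interval and not of patients.

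**Step 3: the same relative rise from different baselines, bilirubin unchanged.** Take a 3.1-fold rise.
- B = 2.5: 2.5 x 3.1 = 7.75. Trigger 7.5 met, cap respected: hold.
- B = 3: 3 x 3.1 = 9.3. Trigger 9 met, cap exceeded: the first row fails. The discontinue row with a bilirubin condition and both bilirubin rows need a bilirubin finding that is absent, and 9.3 is not above 20. No row applies.
- B = 5: 5 x 3.1 = 15.5. Same result.

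**Step 4: does another table fill the gap?**
- Table 6-1 does not, because it excludes ALT/AST.
- Table 6.6 is reachable: more than 3B is more than 9 at B = 3 and more than 15 at B = 5, with no cap. It depends, however, on suspicion of immune-related hepatitis after other causes, including medications, are ruled out. Table 6.5 covers rises attributed to regorafenib.
- The 500 U/L trigger in Table 6.6 carries the same condition. The documents give no ULN; if it is assumed to be 35 to 55 U/L, 500 U/L is 500/35 = 14.3 down to 500/55 = 9.1 x ULN. At B = 3 the 3-fold trigger (9 x ULN) comes first throughout that range.

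**Step 5: alternative reading.** If a 3-fold increase means adding three times the baseline, the trigger is 4B. Then 4B <= 8 needs B <= 2, and the branch is empty for every baseline it is written for. Table 6.6 speaks of a rise to more than 3 times baseline, which supports 3B. The 3B reading is used here and is the more favourable one to the plan.

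**The case against.** The strongest reply is that these patients are not without protection. That is right. The hold for bilirubin above 3.0 mg/dL, the discontinue row that combines ALT/AST with bilirubin, the discontinue row above 20 x ULN and the Table 6.6 interruption all remain reachable. A reader might infer that no regorafenib hold rule exists for patients with liver metastasis; the documents do not support that. The gap concerns isolated ALT/AST rises in a limited baseline range.

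A second reply is that the general instruction for grade 3/4 rises implies an interruption. It does presuppose one. But it orders none, and it gives no rule for resuming or reducing. It shows that the authors expected a hold which, for these patients, no ALT/AST-only row supplies.

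A third reply is that the point overlaps the missing row between 8 and 20 x ULN. This stands. The triggers at issue run from above 8 to 15 x ULN, wholly inside that band, so one repair can serve both.

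Three further inferences should not be drawn:
- A near-doubling without action, such as 4 to 7.9 x ULN (7.9/4 = 1.98-fold), is not caused by the cap, because it fails the 3-fold trigger in any case. That multiple appears in both Table 6.5 and Table 6.6 and looks deliberate.
- The fixed 5 x ULN limit in the row that combines ALT/AST with bilirubin may seem strict for a raised baseline. No other part of the plan contradicts it, and it is a clinical choice.
- The documents do not show that the affected patients have the least hepatic reserve. Criterion 7 also restricts bilirubin, and INR apart from patients on anticoagulation.

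**Conclusion.** The point holds in a limited form. For patients with liver metastasis and an eligible baseline above 2.67 and up to 5 x ULN, the elevated-baseline branch of the first row of Table 6.5 cannot be satisfied. For an isolated ALT/AST rise considered related to regorafenib, that table gives them no reachable hold row below the discontinuation row above 20 x ULN. Table 6.6 applies the same multiple uncapped, so the two tables disagree on whether a 3-fold rise from these baselines calls for interruption.

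The result rests on reading the trigger as 3 times baseline and on the cap applying to the elevated-baseline branch, as the row's wording has it. The number of patients affected is unknown, since no baseline distribution is given. The conflict bears on safety conduct and possibly on treatment duration. It does not touch the sample size or the primary analysis, and it should be corrected.

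**What to change.** Reconcile four places: criterion 7 in section 5.1.1, the general instruction above Table 6.5, the first row of Table 6.5, and the elevated-baseline trigger in Table 6.6. For every baseline that criterion 7 admits, either the trigger and the cap of the first row must be capable of holding together, or values above the cap must be assigned to a row. Handle this together with the missing 8 to 20 x ULN row. The clinical team sets the values and the actions; none is proposed here.

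The cost is table wording in the next amendment. No new tests are needed, because the metabolic panel (CMP) is already scheduled at screening and at treatment visits.
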